#### **15.10.1 Reporting a Study Halt**

If a halting rule is met, a description of the AE(s) or safety issue must be reported by the PI within 1 business day to the CSO, the IRB/EC, and the DSMB by fax or email.

#### **15.10.2 Resumption of a Halted Study**

The IND sponsor, in collaboration with the PI and the DSMB, will determine if it is safe to resume the study. The conditions for resumption of the study will be defined in this notification. The PI will notify the IRB/EC of the decision on resumption of the study.

### 15.11 Discontinuation of Study

The NIAID/Office of Clinical Research Policy and Regulatory Operations (OCRPRO) as the study sponsor, the NIH IRB, FMPOS EC, and the FDA may terminate this study at any time. Reasons for terminating the study may include, but are not limited to, the following:

- The incidence or severity of an AE in this or other studies indicates a potential health hazard to subjects.
- Subject enrollment is unsatisfactory.
- Data recording is inaccurate or incomplete.
- Investigators do not adhere to the protocol or applicable regulatory guidelines in conducting the study.

### 15.12 Withdrawal Criteria for an Individual Participant

A subject will not be considered to have completed the trial if any of the following reasons apply; note Year 1 and Year 2 will be evaluated independently given time between dosing:

1. *Research terminated by Sponsor or Investigator* – applies to the situation where the entire study is terminated by the Sponsor or Investigator, or other regulatory authority for any reason.
2. *Withdrawal of consent* – applies to a subject who withdraws consent to participate in the study for any reason. The investigator will attempt to determine the reason for the subject's decision and document it in the study chart.
3. *Non-compliance with protocol* – applies to a subject who does not comply with protocol-specific visits or evaluations on a consistent basis, and to the extent that it is potentially harmful to the subject or to the integrity of the study data. This also applies to a subject who is lost to follow-up and is not reachable by telephone or other means of communication and cannot be located.
4. *Developed an AE* – applies to a subject who is withdrawn from study due to an AE, serious or otherwise. Any grade 3 or greater AE that is assessed as possibly, probably, or definitely related to vaccination (other than local reactions lasting <72 hours, or systemic reactions lasting <24 hours) will result in withdrawal of the subject from further vaccinations. Subjects may also be withdrawn for ANY AE that would cause continued participation in the study to not be in the best interest of the subject, as per the investigator's judgment. Any subject who is withdrawn from the study because of an AE related to study agent will be followed for safety until at least resolution of that AE and will be encouraged to remain in the safety evaluation for the duration of the study.

5. *Other* – is used when previous categories do not apply and a written explanation is required.

If a subject withdraws or is withdrawn prior to completion of the study, the reason for this decision will be recorded in the source documents and CRFs. Any subject who has received at least 1 dose of vaccine will be encouraged to remain in the safety evaluation for the duration of the study. The subject's data will be included in the safety and immunogenicity analysis. If a subject fails to complete all planned vaccinations because of an AE or SAE, the subject will be followed until resolution or stabilization of the event. If a subject withdraws, the investigator will make a reasonable effort to determine the reason.

#### **15.12.1 Replacement of Withdrawn Participants or Participants Who Discontinue Study Agent**

Subjects who have received at least 1 vaccination and who withdraw or are terminated from the study prior to completion will not be replaced. Subjects withdrawn before the first vaccination may be replaced.

### **15.13 Safety Oversight**

#### **15.13.1 Safety Review and Communications Plan**

A Safety Review And Communications Plan (SRCP) has been developed for the protocol. The SRCP is an internal communications document between the PI and the CSO, which delineates the safety oversight responsibilities of the PI, the CSO, and other stakeholders. The SRCP also includes the overall plan for conducting periodic safety surveillance assessments.

#### **15.13.2 Sponsor Medical Monitor**

A medical monitor, representing the IND sponsor (OCRPRO), has been appointed for oversight of safety in this clinical study. The sponsor medical monitor will be responsible for performing safety assessments as outlined in the SRCP.

#### **15.13.3 Independent Safety Monitor (ISM)**

An ISM in Mali will review the study prior to initiation and will be available to advise the Investigators on study-related medical issues and to act as a representative for the welfare of the subjects. The ISM will conduct independent safety monitoring and recommend appropriate action regarding AEs and other safety issues. The ISM is an expert in the field of oversight of clinical trials conducted in Mali and internal medicine, specifically in the population under study in Mali. The ISM does not have direct involvement in the conduct of the study and does not have other interests with any collaborating pharmaceutical firms or their competitors.

Prior to each ISM review (including DSMB meeting safety reports and at least twice yearly reviews), the PI will provide a safety summary report (similar to the DSMB safety reports). After each ISM review, a recommendation as to whether the study is to be modified or terminated will be provided in a summary report to the study PI. If the study is to continue as is, no report will need to be submitted by the ISM except for communication to the PI that the review has been completed (via in-person communication, phone, or email). All SAEs, all UPs, and all IND Safety Reports will be reported by the PI to the ISM at the same time they are submitted to the IRB/EC or IND sponsor. The ISM will be notified immediately if any pausing or halting rule is met and the ISM will provide recommendation for continuation, modification, or termination of the study. The PI will submit the written ISM summary report with the recommendations to their IRB/EC on a biannual basis or more frequently if a safety concern is raised.

#### **15.13.4 Data and Safety Monitoring Board (DSMB)**

The NIAID intramural DSMB includes independent experts that do not have direct involvement in the conduct of the study and have no significant conflicts of interests as defined by NIAID policy. The DSMB will review the study prior to initiation and at the end of the study, and may convene additional reviews as necessary. The board will review the study data to evaluate the safety, efficacy, study progress, and conduct of the study as denoted in [Figure 23](#) and [Figure 24](#). All SAEs, all UPs, and all IND Safety Reports will be reported by the PI to the DSMB at the same time they are submitted to the IRB or IND sponsor. The PI will notify the board at the time pausing or halting criteria are met and obtain a recommendation concerning continuation, modification, or termination of the study. The PI will submit the written DSMB summary reports with recommendations to the IRB/EC.

### **16 Site Monitoring Plan**

According to the International Conference on Harmonisation (ICH) E6(R2) Good Clinical Practice (GCP) guidelines, section 5.18, and FDA 21 CFR 312.50, clinical protocols are required to be adequately monitored by the study sponsor. This study monitoring will be conducted according to the “NIAID Intramural Clinical Monitoring Guidelines.” Monitors under contract to the NIAID/OCRPRO will visit the clinical research site to monitor aspects of the study in accordance with the appropriate regulations and the approved protocol. The objectives of a monitoring visit will be: 1) to verify the existence of signed informed consent documents and documentation of the consent process for each monitored subject; 2) to verify the prompt and accurate recording of all monitored data points and prompt reporting of all SAEs; 3) to compare abstracted information with individual subjects’ records and source documents (subjects’ charts, laboratory analyses and test results, physicians’ progress notes, nurses’ notes, and any other relevant original subject information); and 4) to help ensure investigators are in compliance with the protocol. The monitors also will inspect the clinical site regulatory files to ensure that regulatory requirements (Office for Human Research Protections [OHRP], FDA) and applicable guidelines (ICH GCP) are being followed. During the monitoring visits, the investigator (and/or

designee) and other study personnel will be available to discuss the study progress and monitoring visit.

The investigator (and/or designee) will make study documents (e.g., consent forms, DataFax data abstracts) and pertinent hospital or clinical records readily available for inspection by the FMPOS EC, FDA, the site monitors, and the NIAID staff for confirmation of the study data.

A specific protocol monitoring plan will be discussed with the PI and study staff prior to enrollment. The plan will outline the frequency of monitoring visits based on such factors as study enrollment, data collection status, and regulatory obligations.

## **17 Statistical Considerations**

### **17.1 Pilot Study**

#### **17.1.1 Primary Objective**

The primary objective of the pilot study is to assess the safety and reactogenicity of Pfs230D1M-EPA/AS01 in Malian children (Arms 1a, 2a) compared to comparator vaccine (Arms 1b, 2b).

- The frequency of systemic and local AEs will be summarized.
- A line listing of each clinical and laboratory AE classified as local, solicited, or other will be displayed in tables stratified by vaccine allocation.
- AEs will be summarized by severity and relationship to vaccine.
- The proportion of subjects with at least 1 AE will be compared by study group, and tests will be performed to assess whether these groups differ with respect to these proportions. To evaluate the difference in AEs between the initial vaccination and the subsequent vaccinations, a Wilcoxon signed rank test (WSRT) will be performed, where the response for each subject is the difference between the numbers of AEs in the 7 days following each vaccination. To compare number and severity of AEs between control and vaccine arms, the Wilcoxon-Mann-Whitney test (WMW, also known as Wilcoxon rank sum test and Mann-Whitney U test) as well as linear regression may be used.
- SAEs occurring within the study period will be listed by relationship to vaccine.

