## **11.2 Assignment to Groups**

### **11.2.1 Pilot Safety Study**

The subjects in Pilot Safety Study will be assigned randomization per their family compound randomization. In order for a compound to qualify for randomization, approximately 80% of the residents within a family compound/vaccine unit who are preliminarily eligible for vaccination must have signed consent and be preliminarily eligible for enrollment (e.g. screening available vaccinee unit for major medical problems, pregnancy, and time availability). When the first child (<19 years of age) from the family compound is scheduled for vaccination, the family compound as a whole will then be randomized to Pfs230D1M-EPA/AS01 or comparator.

The Pilot Study cohorts will be enrolled in the following order:

1. Arms 1a (n=15) and 1b (n=15); then
2. Arms 2a (n=15) and 2b (n=15)

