## 17.3 Sample Size and Power Calculations

### 17.3.1 Pilot Study

#### 17.3.1.1 Safety

The arms are sufficiently sized for safety. For each dose level ( $n=15$ ) in Arms 1a, 2a, vaccination of 15 subjects gives a probability of at least 0.90 for detecting 1 or more serious or severe AEs that occur with a probability of 0.142 or more per subject.

If we combine all treated groups (arms 1a and 2a), 30 subjects, we have 95% power to detect 1 or more serious or severe AEs that occur with a probability of 0.095 or more per subject. Due to arms having different age ranges, this analysis would only be done to catch an AE that transcended these discrepancies.

We will compare all AE event proportions between the control arm and treated arm by Fisher's exact test.

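### The any-AE comparison has no AE class, relatedness or time window; if children resemble the earlier adult trial it is uninformative in the pilot and insensitive within the main-study age groups

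*Combined protocol and SAP*

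**What the plan says.** The pilot's primary safety objective (17.1.1) is vaccine against comparator. After summaries of AEs by type, severity and relationship, it commits to one between-group test of proportions: "The proportion of subjects with at least 1 AE will be compared by study group". Section 17.2.2 repeats this for the main study. No window, AE class, grade, relatedness, test or alpha is attached. The 7-day window in the next sentence belongs to a within-subject comparison of doses. A further between-arm analysis is optional: "To compare number and severity of AEs between control and vaccine arms, the Wilcoxon-Mann-Whitney test", or linear regression, may be used.

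The pilot sizing section (17.3.1.1) opens with "The arms are sufficiently sized for safety" and supports that with detection probabilities: "vaccination of 15 subjects gives a probability of at least 0.90 for detecting 1 or more serious or severe AEs" at a rate of 0.142 and, with n = 30 after pooling both age groups, "we have 95% power to detect 1 or more serious or severe AEs that occur with a probability of 0.095 or more per subject". It then adds "We will compare all AE event proportions between the control arm and treated arm", using Fisher's exact test. For the main study, 17.2.3 and 17.3.2.3 add GEE and cluster-respecting analyses of safety endpoints and AE rates, without naming the endpoints.

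**The concern.** A subject counts as having an AE whatever its nature. Section 15.3 keeps recording unsolicited AEs, symptomatic malaria included, after day 7, and 15.3.2 classes every malaria case as unrelated to vaccination. In Table 8, malaria AEs after dose 3 alone affected 135/210 (64.3%) of the 5-8 year-olds and 282/386 (73.1%) of the 9-18 year-olds, arms combined. Background illness can therefore push the any-AE proportion close to 100% in both arms and leave no room for a vaccine effect to show.

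At stake is how a null result is read. A non-significant any-AE comparison, next to a statement that the arms are large enough for safety, could be taken as similarity to licensed vaccines when the variable could not have shown a difference.

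**Working it through.** **Plan's own figures.** The chance of seeing at least one event is 1 - (1 - p)^n.
- n = 15, p = 0.142: 1 - 0.858^15 = 0.899, stated as 0.90.
- n = 30, p = 0.095: 1 - 0.905^30 = 0.950, stated as 0.95.

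Both reproduce. Both are chances of observing an event in vaccinees; neither is power to compare arms.

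**Inputs.** Subject counts come from Table 3 (primary series, full dose vs control) and Table 5 (fourth dose) of the predecessor adult trial. Table 5's caption mentions seven days, but its totals are the 363 and 305 AEs that Section 3.2.2 describes, which include malaria and rhinitis. Two-sided alpha of 0.05 and Fisher's exact test are assumed, since the plan names neither for this comparison.

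**The comparison applied to the earlier data.**

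| Outcome | Vaccine | Control | Difference | Fisher p |
|---|---|---|---|---|
| Any AE, primary series | 55/56 (98.2%) | 113/120 (94.2%) | +4.0 points | 0.44 |
| Local, primary series | 51/56 (91.1%) | 31/120 (25.8%) | +65.3 points | about 1e-16 |
| Any AE, dose 4 | 78/82 (95.1%) | 80/80 (100%) | -4.9 points | 0.12 |
| Local, dose 4 | 49/82 (59.8%) | 14/80 (17.5%) | +42.3 points | 3e-8 |

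The fractional-dose arm gives the same picture for any AE: 59/60 vs 113/120, p = 0.27. At dose 4 the any-AE difference runs the other way.

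**Pilot power.** Arm sizes are from 11.2.1 ("1. Arms 1a (n=15) and 1b (n=15); then", and the same for Arms 2a and 2b), so 15 per arm by age group and 30 per arm pooled. Power is the sum, over all pairs of binomial outcomes with Fisher p at or below 0.05, of their joint probability.

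| True rates | 15 per arm | 30 per arm |
|---|---|---|
| Any AE, 98% vs 94% | 0.1% | 0.4% |
| Any AE, 100% vs 94% | 0.1% | 0.8% |
| Local, 91% vs 26% | 95% | >99.9% |
| Local at dose 4, 60% vs 18% | 50% | 89% |
| Systemic, 16% vs 2% | 6% | 22% |

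Even if every vaccinee has an AE, significance needs 5 of 15 controls with none (p = 0.042; 4 gives 0.100) or 6 of 30 (p = 0.024; 5 gives 0.052). If 6% of controls are AE-free, the chance of that is 0.14% and 0.8%.

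**Main-study power.** Vaccinated counts in 3.3.1 (pilot children included) are 213, 398 and 490, total 1101. Halving them, with 1:1 assumed and clustering ignored, gives the sizes below.

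| Stratum | Per arm | 98% vs 94% | 99% vs 97% |
|---|---|---|---|
| 5-8 years | 107 | 19% | 4% |
| 9-18 years | 199 | 44% | 17% |
| 19 years and over | 245 | 55% | 23% |
| All ages | 550 | 92% | 60% |

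**The case against.** The strongest reply is that this is one comparison among several. Section 17.3.1.1 commits the pilot to Fisher's test on all AE event proportions; read event by event, that has 95% power at 15 per arm for the local contrast. The pilot endpoint (8.1.1) is the incidence of local and systemic AEs and SAEs. The main study adds clustered analyses. Pausing and halting rules (15.9, 15.10) use related and graded events, mostly within 7 days, not the any-AE proportion. The protocol's own account of the adult trial reports local and systemic reactogenicity by symptom, grade and dose and draws no reassurance from the any-AE row. This stands: a reader might infer that any-AE is the only safety test and that a strongly reactogenic vaccine would go unnoticed, and the documents do not support that.

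A reader might also infer that a non-significant result is nearly certain throughout the trial. That holds only at pilot size; the pooled main study has about 92% power at 98% vs 94%.

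Third, the 94-100% rates come from adults with other comparators. No any-AE proportion is reported for these children. If the 7-day window were meant to apply, saturation would not follow: Table 4 puts Grade 1 injection-site pain in controls at 4-18% per dose.

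Last, class-specific tests are not a cure-all, as the 6% and 22% for systemic events show. That argues for intervals and a plain statement of power, not for keeping any-AE as a tested outcome. Nor does the event-by-event reading settle the matter: the sentence names no events or window, sits only under pilot sizing, and is not repeated for the main study.

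**Conclusion.** The point holds in a limited form. As written in 17.1.1 and 17.2.2, the any-AE comparison is uninformative in the pilot (power below 1%) and insensitive within main-study age groups (19-55% at 98% vs 94%). Pooled, it can reach significance, yet would show a gap of about 4 points where local reactogenicity differed by 65. This rests on children having any-AE rates like the adults', counting over full follow-up, Fisher's test at two-sided 0.05, 1:1 allocation at the vaccinated counts, and no allowance for clustering, which favours the plan. The pilot sizes are adequate for a local contrast as large as the adult primary series; the weakness there is the chosen variable. The defect is worth correcting but does not leave the trial without a safety comparison.

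**What to change.** In 17.1.1 and 17.2.2, replace the tested any-AE proportion with three: at least one solicited local AE within 7 days of vaccination, at least one solicited systemic AE within 7 days of vaccination, and at least one related AE of Grade 2 or higher. Give arm differences with 95% CIs, exact in the pilot and allowing for vaccine-unit clustering in the main study. Report Grade 3 or higher AEs with CIs. Keep any-AE as a descriptive row.

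In 17.3.1.1, state that the pilot has adequate power for local reactogenicity (95% at 15 per arm for 91% vs 26%) but little for systemic events (6% at 15 and 22% at 30 per arm for 16% vs 2%), and that a non-significant pilot result must not be read as similarity.

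The cost is revised wording and a few table rows. Solicited status, timing, grade and relatedness are already collected under Section 15.3.

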#### **17.1.2 Secondary Objective**

The secondary objectives of this study are:

- To assess ELISA titer response to Pfs230D1M-EPA/AS01 in Malian children (Arms 1a, 2a)
- To assess functional antibody response by SMFA to Pfs230D1M-EPA/AS01 in Malian children (Arms 1a, 2a)

Anti-Pfs230 antibody will be measured by ELISA on vaccination days, 2 weeks after each vaccination, and periodically until study completion. Antibody responses over time will be shown graphically with geometric mean antibodies and the associated confidence intervals based on the t-distribution applied to the log-transformed responses. We will compare antibody and functional assay responses within arms over time. We will also look at differences in antibody decline over time in the vaccination groups. Graphs will display transmission-blocking assays as a function of ELISA antibody levels.

### 17.1.3 Exploratory Objective

The exploratory objective of this study is:

- To explore cellular responses and antibody repertoire of functional antibody responses to vaccination (all arms)

We will characterize and compare host immune responses and antibody repertoires to malarial antigens and to vaccine antigens in African children prior to and after vaccination with Pfs230D1M-EPA/AS01 by mixed effects model or WSRT depending on the type of immune response. We will also make figures depicting immune response based on the study arm.

Should the study be terminated early, the investigative team will discuss with the DSMB the reason for termination and determine which study questions can be addressed in an unbiased manner with the available data. The available data will be analyzed and interpreted in light of early termination.

## 17.2 Main Study

### 17.2.1 Primary Objective

To assess vaccine activity of Pfs230D1M-EPA/AS01 against *P. falciparum* transmission by direct skin feeding assay (DSF) (Arms 1a/1b and 3c/3d only)

A Poisson type model with compound level clustering with offset for the number of DSF tests that were performed will be used. The primary analysis of activity measured by DSF will be the Poisson GEE, which will be performed on the data once with Pm/Po midguts, and once without. The proportion of subjects infecting at least 1 mosquito in at least 1 DSF over the primary analysis period following dose 3 will be compared by use of a GEE model for binary response with compound level clustering.

Each of the above analyses will be performed on the subsample of subjects that had a concurrent positive BS (any parasite sexual and/or asexual) or rapid test positive with their DSF results.

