##### **1.2.3.1.1.1 Local, Seasonal Transmission**

There is evidence, that includes different types of studies (described in the **Section of 1.2.2**), that malaria transmission occurs at a very local scale, that is, that the distance between the locations where mosquitoes acquire infection and where they feed after *falciparum* parasite sporogonic development, potentially inoculating sporozoites in uninfected individuals, is on average small. This key epidemiological observation provided the basis for the selection of compounds as units of randomization and analysis in this clinical trial, as the impact of transmission blocking vaccines is likely to be most evident at this scale.

One of the determinants of the spatial scale in which malaria transmission occurs is the distribution of mosquito breeding sites. Between blood meals, *Anopheles* mosquitoes lay eggs on water bodies, and the distance traveled for oviposition will depend on the presence of nearby breeding sites. During the rainy season, in areas with endemic malaria transmission, including in the village where this vaccine trial is being performed, the number of temporary breeding sites and their larval productivity increases, as observed in entomological studies across different settings and respective colleagues observed that the frequency of aquatic habitats and their stability were influenced by rainfall. This more widespread distribution of potential oviposition sites implies a high likelihood that there will be nearby breeding sites for mosquitoes ovipositing after feeding in study compounds/vaccine units. It is thus during this period that circulation of parasites within vaccine units (which may be one or more compounds) is expected to be highest (i.e. infected mosquitoes biting individuals living in the same compound/vaccine unit where they acquired their infection). As explained in detail in **Section 1.2.2**, there is

[figure not shown]
evidence from epidemiological studies in Mali that the degree of locality of malaria transmission varies seasonally (**Figure 5**).

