#### 8.4 Study Definitions

**Screened:** Subjects will receive a screening identification number (SC-XXX-XXX) when the informed consent is signed, and will either be determined as “enrolled” or “screen failures” as noted below; subjects within the same vaccine unit will be noted by the same first 3 numbers (SC-XXX-xxx) of their screening identification.

- Screening may be completed over the course of multiple visits.
- Screening will occur within 56 days prior to enrollment into the study.
- If the screening visit is >56 days prior to enrollment (determined by the date of each component), then an updated medical review, physical exam/vital signs, repeat Malaria Comprehension Exam, and repeat laboratory evaluation (inclusive of safety labs, human immunodeficiency virus [HIV], EKG) will be completed to determine eligibility for enrollment.

**Enrolled:** Subjects will be considered enrolled beginning with the receipt of the first blood draw and first AL dose.

- Final study number assigned – MV-19-XXX-XXX-X [MV-19-(vaccine unit #)-(study # per age)-(letter for QC)]
  - Given the last three numbers of the study number are dependent on age and requirement by the electronic database to have a study number during screening, if a child/young adult changes age categorization (4→5-year-old, 8→9-year-old, 18→19-year old) between screening and enrollment a new study ID will be assigned categorizing the study subject as above. The screening identification number will not change.

**Randomized:** Subjects are considered randomized when their family compound/vaccine unit undergoes randomization collectively at the time of first vaccination of their first family member. A compound/family may be randomized once the following criteria are met:

- Approximately 80% of the family compound/vaccine unit preliminarily eligible to be vaccinated has signed consent, agreed to participate in the study, and has been found preliminarily eligible for enrollment
- Entire family/compound will be randomized as a collective whole at the time of first vaccination in any family compound/vaccine unit participant
- To note: prior to the start of the study, the study geographers, based off GPS coordinates and village census assigned family compounds into vaccine units which were randomized as a unit.

**Re-enrolled:** Subjects are considered re-enrolled for Year 2 of follow-up when they complete the following:

- Re-consent

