**Figure 29: Maps Showing the Location of Doneguebougou, Mali.**

(A) In reference to other West African countries and within Mali; (B) Context of location of Doneguebougou and Sirababougou to one another.

A family compound in Mali is a composite of different houses, and members are usually related by paternal relationship. The family compound can contain members of several related generations and be as large as 100+ or as small as 5-10. The family compound has a chief of family (usually the oldest man), while houses within the family compound are led by the chief of the household (usually the husband of the household). Important decisions are typically made by the chief of family. Spatial distribution and categorization of inhabitants by family compounds in Doneguebougou are provided below in [Figure 30](#). As noted prior, a single family compound may compose a single vaccine unit or multiple family compounds may compose a single vaccine unit.

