### 17.3.2.3 Analysis

The primary DSF analysis will use a GEE model with compound level clustering and the number of positive DSFs as outcome will be used for analysis with an offset for the number DSF tests. The primary parasitemia analysis will be analogous. The primary analysis population will follow the intention-to-treat principle. Additional analyses will explore the effects of different covariates such as time since start of the rainy season, SMC treatment, compound-level vaccine coverage, or proximity to a control compound on vaccine efficacy.

The primary safety and immunogenicity analyses will compare the rates of AEs or levels of antibody/activity between vaccinated and control individuals using standard statistical methods that respect compound-based randomization, as appropriate.

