### 17.4 Randomization

See [Section 11.2](#) for more information on individual study schedule.

This study will be cluster-randomized with family compounds, or groups of compounds (vaccine units) serving as the unit of comparison. A listing of the compounds in the study area with the numbers of individuals residing in their compounds will be created and used for randomization. The number of vaccine units will be the similar for each group. Enumerated compounds should have a target of approximately 80% participation rate of eligible participants for inclusion as a study unit, but consideration will be given to the number of children to finalize the decision for inclusion. Randomization for the full trial needs to be completed prior to the age de-escalation so that the randomization for vaccinated participants in the pilot phase study holds through the main phase.

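### The GEE models cluster on the compound, but the randomised unit is the vaccine unit, which may hold several compounds; the plan should name the vaccine unit as the cluster.

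*Combined protocol and SAP*

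**What the plan says.** Three places describe what was randomised. Section 8.4 reports that geographers, before the study began, "assigned family compounds into vaccine units which were randomized as a unit". Section 9.1 adds that "a single family compound may compose a single vaccine unit or multiple family compounds may compose a single vaccine unit". Section 17.4 calls the trial "cluster-randomized with family compounds, or groups of compounds (vaccine units) serving as the unit of comparison", which distinguishes a single compound from a group of compounds.

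The models are written one level down. Section 17.2.1 has: "A Poisson type model with compound level clustering with offset for the number of DSF tests that were performed will be used". The binary DSF model in the same section also clusters by compound. Section 17.3.2.3 restates it: "The primary DSF analysis will use a GEE model with compound level clustering and the number of positive DSFs as outcome", and says that the parasitemia analysis is analogous. Section 17.2.3 names a compound-clustered GEE for ELISA, SMFA and safety endpoints. No GEE statement names the vaccine unit.

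For main-study adverse events, Section 17.2.2 says that Wilcoxon-Mann-Whitney or linear regression may be used for arm comparisons of number and severity. Section 17.3.2.3 asks for safety methods that respect the compound-based randomisation.

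**The concern.** A robust (sandwich) variance sums over clusters that it takes to be independent. If the cluster is the compound, any covariance between two compounds of the same vaccine unit is left out. Those compounds always share an arm, so a positive covariance adds to the true variance of the arm contrast and its omission makes the standard error too small.

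The protocol itself argues that the covariance is positive. Section 1.2.2 reports raised infection odds in households neighbouring a case, and rainy-season clusters spanning one or a few adjacent compounds. Section 8.4 says that GPS coordinates were used to form the units. At stake are the width of the primary confidence interval and the level of the primary test. A programmer following 17.2.1 to the letter would use the compound as cluster ID.

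**Working it through.** **Inputs from the plan (Section 17.3.2.1 unless noted)**
- Intra-compound correlation ρ = .01, estimated for parasitemia in Bancoumana and used as a proxy for DSF.
- Median children aged 9-18 per compound, m = 4.
- Intra-subject correlation for serial feeds, .14.
- Per-feed positivity in Year 1, 2.4% (70 of 2875; Section 3.3.3).
- Children aged 9-18 enrolled, 399 (Table 12).

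**Assumed, because the plan does not give them**
- Compounds per unit, k = 1, 2 or 3.
- The same ρ within and between compounds of a unit.
- ρ = .05 as an alternative value.

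**The plan's own statement.** The compound-level design effect is 1 + (m − 1)ρ = 1 + 3 × .01 = 1.03. This agrees with the plan's description of clustering as negligible at that level.

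**Moving to the randomised unit**
- Unit-level design effect = 1 + (km − 1)ρ.
- SE ratio (true over compound-clustered) = √(unit design effect / compound design effect).
- Actual two-sided type I error = 2[1 − Φ(1.96 / SE ratio)].

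| ρ | k | Design effects, unit / compound | SE ratio | Type I error |
|---|---|---|---|---|
| any | 1 | equal | 1.00 | 5.0% |
| .01 | 2 | 1.07 / 1.03 | 1.019 | 5.4% |
| .01 | 3 | 1.11 / 1.03 | 1.038 | 5.9% |
| .05 (assumed) | 2 | 1.35 / 1.15 | 1.083 | 7.0% |
| .05 (assumed) | 3 | 1.55 / 1.15 | 1.161 | 9.1% |

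**Simulation check.** Null trials (4000 per scenario) used 400 children, 100 or just under 100 compounds, 8 feeds, 2.4% positivity and intra-subject correlation .14. The test was a Poisson rate ratio with robust variance. The Monte Carlo standard error near 5.5% is √(.055 × .945 / 4000), about 0.4 percentage points.
- ρ = .01: rejection 5.7% clustering on compound against 5.8% on unit (k = 2), and 5.9% against 6.2% (k = 3). Mean SE ratios were 1.01 and 1.02.
- ρ = .05: 6.9% against 5.6% (k = 2), and 8.5% against 6.0% (k = 3).

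At .01 compound clustering therefore shows no measurable excess over unit clustering. At .05 it does.

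**Plausible unit size.** Section 12.11 describes one male and one female selected from each participating unit, with 101 participants in all, so about 101 / 2 ≈ 50 units in that subgroup alone. With at least about 50 units, the mean is at most 399 / 50 ≈ 8 children per unit, or two compounds of four. Three compounds of four in every unit would mean only 399 / 12 ≈ 33 units. If the planned 137 is the number of vaccine units, the mean is 399 / 137 ≈ 2.9 children. With about 1.5 children per compound and k = 2, ρ = .01 gives √(1.02 / 1.005) = 1.007 and a type I error of 5.2%.

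**The case against.** The strongest reply is that compound is often shorthand here for the randomised unit. The Protocol Summary and Sections 7.1 and 8.4 write compound/vaccine unit as one term. Section 7.2.2 describes about 30 compounds/vaccine units enrolled as waves of 5, 10 and 15 compounds. Section 1.2.3.1.1.1 speaks of the "selection of compounds as units of randomization and analysis in this clinical trial". On that reading the GEE already clusters on the right unit. This stands as a possible reading, but it is not stated, and Section 17.4 separates the two terms. One sentence would settle it.

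The second reply is size. At the only correlation that the plan gives, the effect is close to nil. This also stands. The .01 is a within-compound parasitemia figure from another village, so it does not exclude a larger unit-level value for DSF, but nothing in the documents supplies one. Equal correlation across compounds is also a high assumption, since Section 1.2.2 reports a weaker association in neighbouring households than in the case household.

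A reader might further infer that adverse event testing ignores clustering altogether, from the line "We will compare all AE event proportions between the control arm and treated arm by Fisher's exact test". That line is in the pilot safety section (17.3.1.1), where arms have 15 children. For the main study, 17.2.3 already names a clustered GEE for safety and 17.3.2.3 calls for methods that respect the randomisation. What remains there is an inconsistency: the optional Wilcoxon-Mann-Whitney comparison in 17.2.2 assumes independent subjects.

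**Conclusion.** The point holds as a mismatch between the randomised unit and the stated GEE cluster. Its direction is clear if units contain more than one compound and the correlation between compounds is positive. Its size on the plan's own figures is small: a standard error about 1-4% too small and a type I error of about 5.4-5.9% with two or three compounds of four children per unit. Error rates of about 7-9% need an assumed correlation of .05, equal across all compounds of a unit.

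The documents do not support the stronger conclusion that the primary p-value is materially anti-conservative. They give neither the compounds per unit nor a unit-level correlation, and the wording may be loose rather than wrong. The case for acting is that the ambiguity concerns the primary analysis and costs almost nothing to remove.

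**What to change.** In 17.2.1, 17.2.3 and 17.3.2.3, state that the GEE cluster is the randomised vaccine unit. If compound was always meant as vaccine unit, the same sentence records that.

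In 17.2.2, replace the Wilcoxon-Mann-Whitney comparison of adverse events between arms with the clustered GEE already named for safety in 17.2.3, with the vaccine unit as cluster.

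Leave Section 17.3.2.1 as a description of a compound-level simulation unless it is rerun; relabelling it would misreport what was simulated.

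If the number of units proves small, a small-sample correction to the robust variance is worth naming too: in the simulation, unit clustering itself rejected 5.6-6.2% of the time with 50 or 32 units at correlations of .01 and .05.

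The cost is a few words in the plan and a change of cluster variable in the code. Section 8.4 shows that the vaccine unit number is already part of the study ID, so no new data are needed. The change should be made before unblinding.
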